9.5 Treatment Accountability and Compliance

The pharmacist or other designated individual will maintain records of study drug delivered to the study site, the inventory at the study site, the distribution to and use by each patient, and the return of materials to the sponsor for storage or disposal. These records should include dates, quantities, batch/serial numbers, expiration dates, in-clinic temperature log, and unique code numbers assigned to the product and patients.

During hospitalization, the administration of the study drug will be performed by the investigator (or qualified blinded designee) to ensure compliance. If the patient is discharged home before Day 28, the study team will provide the patient with the remainder of the assigned blinded study drug kit(s) to take home along with instructions to continue treatment at home; for these patients, treatment compliance will be conducted via a diary. If the patient does not feel comfortable to complete the diary, the site will alternatively provide the patient with the option to be called, twice a day, to confirm that the study drug is taken as instructed. Patients are to be reminded of the importance of compliance with their assigned regimen, with an emphasis on taking their study drug on schedule and maintaining the prescribed interval between doses.

Investigators will maintain records that adequately document that the patients were provided with the correct study drug kit(s) and reconcile the products received from the drug dispensing center. Investigational product will not be returned to the sponsor until accountability has been fully monitored.

Noncompliance is defined as taking <80% or >120% of study drug. Discontinuation for noncompliance is at the investigator's discretion and is to be noted on the eCRF.

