Provide remainder of the assigned blinded study drug kit(s) to the patient along with instructions ¹	-	-	-	-		-	-	X (only if discharged during the treatment period; NA for Early Study Termination)
Provide patient with the diary and train patient on use of the diary ¹	-	-	-	-		-	-	X (only if discharged during the treatment period; NA for Early Study Termination)
COVID-19 symptoms	Х	Х	-	Х		Х	Х	Х
COVID-19 severity ^o	Х	Х	-	-		-	-	-
Clinical status related to COVID-19 on the NIAID 8-point ordinal scale ^p	Х	Х	Х	Х		Х	Х	Х

MetrioPharm AG
MP1032

MP1032-CT05 Protocol v2.0 - Bulgaria

Study Period	Screening Period			Treatm	ent Period		Follow-up Period	-
Visit Name	Screening ^a	Day 1ª	Days 2 to 13 ^b	Day 14 ^b	Day 21 ^b	Day 28 (End of Treatment Visit) ^b	(Follow-up Visit) ^b / Early Study	Day of Discharge / Early Study Termination before Day 28 ^b
Study Day (window)	Day -7 to Day -1	Day 1 (NA)	Days 2 to 13 (NA)	Day 14 (±2 days)	Day 21 (±2 days)	Day 28 (±3 days)	Day 60 (±3 days)	Day of Discharge
EQ-5D-5L questionnaire ^q	-	-	-	-		-	х	X (only if discharged/ early terminated before Day 60)
Blood sample collection (plasma) for PK (from the PK subset of approximately 30 patients who give optional consent) ^m	-	Х	X (only Day 7) ⁱ			-	-	-
AEs	X					Х		
Prior and concomitant medications		Х				Х		

Abbreviations: AE = adverse event; BID = twice daily; BMI = body mass index; COVID-19 = coronavirus 2019; ECG = electrocardiogram; eCRF = electronic case report form; EQ-5D-5L = EuroQol-5D-5L; IEC = independent ethics committee; ICU = intensive care unit; IRB = institutional review board; IWRS = interactive web-response system; LAR = legally authorized representative; NA = not applicable; NIAID = National Institute of Allergy and Infectious Diseases; PK = pharmacokinetic; RT-PCR = reverse transcription-polymerase chain reaction; SAE = serious adverse event; SARS-CoV-2 = severe acute respiratory syndrome coronavirus type 2; SoC = standard of care; $SpO_2 =$ saturation of oxygen; WOCBP = women of childbearing potential.

a. Those patients who are fully eligible (all screening assessments are available) can have Day 1 performed on the same day as screening. If screening and Day 1 are performed on the same day, visit procedures required for both visits do not need to be repeated.

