1 EFFICACY ASSESSMENTS

The Schedule of Assessments (Table 1) outlines the efficacy assessments to be performed throughout the study and their timing.

This document is confidential.

Page 53 of 89

MetrioPharm AG	MP1032-CT05
MP1032	Protocol v2.0 - Bulgaria

1 COVID-19 Symptoms

The assessment of the COVID-19 symptoms will be recorded at the visits specified in the Schedule of Assessments (Table 1).

The patient will be assessed for the following as shown in Table 2.

Table 2COVID-19 Symptoms

Symptom	Response Options and Scoring
1. Stuffy or runny nose	
2. Sore throat	
3. Red or irritated eyes (conjunctivitis)	
4. Shortness of breath (difficulty breathing)	
5. Cough	None = 0
6. Low energy or tiredness	Mild = 1
7. Muscle or body aches	Moderate = 2 Severe =3
8. Headache	Severe -5
9. Chills or shivering	
10. Feeling hot or feverish	
11. Nausea (feeling like you wanted to throw up)	
12. How many times did you vomit (throw up) in the last 24 hours?	I did not vomit at all = 0 1-2 times = 1 3-4 times = 2 5 or more times = 3
13. How many times did you have diarrhea (loose or watery stools) in the last 24 hours?	I did not have diarrhea at all = 0 1-2 times = 1 3-4 times = 2 5 or more times = 3
14. Rate your sense of smell in the last 24 hours.	My sense of smell is THE SAME AS usual = 0 My sense of smell is LESS THAN usual = 1 I have NO sense of smell = 2
15. Rate your sense of taste in the last 24 hours.	My sense of taste is THE SAME AS usual = 0 My sense of taste is LESS THAN usual = 1 I have NO sense of taste = 2

Note: Score values are included in the table for ease of reference. Score values within the response options will not be presented to patients to avoid confusing patients.

12 COVID-19 Severity

The assessment of the COVID-19 severity will be recorded at the visits specified in the Schedule of Assessments (Table 1). As per the inclusion and exclusion criteria (see Section 8.1 and Section 8.2), patients who are randomized must have either moderate or severe COVID-19. The criteria (FDA 2020) used to determine the patient's COVID-19 severity incorporates objective measures as follows:

MetrioPharm AG	MP1032-CT05
MP1032	Protocol v2.0 - Bulgaria

MP1032-CT05

Final

Asymptomatic SARS-CoV-2 infection

- Positive SARS-CoV-2 testing by standard RT-PCR assay or equivalent test
- No symptoms

Mild COVID-19

- Positive SARS-CoV-2 testing by standard RT-PCR assay or equivalent test

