A similar analysis of covariance approach as described above for Day 28 will be applied for the analysis of the change of clinical status related to COVID-19 on Day 14 compared with baseline on the NIAID 8-point ordinal scale. The endpoint considering the proportion of patients requiring invasive ventilation (mechanical ventilator and/or ECMO) or who are not alive, the proportion of patients in each NIAID category, and the proportion of patients alive and testing negative for COVID-19 on Day 14, Day 28, and Day 60, respectively, will be compared between the treatment groups using MH test. Overall survival, time to (first) improvement of at least 1 category on the NIAID scale and total hospitalization duration (from baseline to discharge; with death censored on last day of the observed period – at Day 28 or Day 60, respectively – depending on the analyses) will be summarized using the Kaplan-Meier method and will be

This document is confidential.

Page 72 of 89

MetrioPharm AG	MP1032-CT05
MP1032	Protocol v2.0 - Bulgaria

compared between treatment groups using log-rank tests. Additionally, Cox proportional hazards model will be applied with treatment and the 2 stratification factors as covariables.

The odds ratio between MP1032 and SoC and placebo and SoC for the number of patients with clinical status improvement from baseline on the NIAID 8-point ordinal scale (ie, an improvement of at least 1 category) at Day 14 and Day 28 will be analyzed using a logistic regression with consideration of the 2 stratification factors.

The time to recovery of all at baseline present COVID-19 symptoms (stuffy or runny nose, sore throat, red or irritated eyes, shortness of breath, cough, low energy or tiredness, muscle or body aches, headache, chills or shivering, feeling hot or feverish, nausea, and number of times of vomit, times of diarrhea, sense of smell, sense of taste in the last 24 hours) will be presented by Kaplan-Meier estimates and figure. The change from baseline will be presented in shift tables for each single symptom, with the number and percentage of subjects in each category at post-baseline assessment time-point compared to baseline for each treatment group.

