- Proportion of patients with disease resolution on Day 14. Disease resolution is defined as patients who are alive and have a score of 6, 7, or 8 on the NIAID 8-point ordinal scale.
- All-cause mortality rate at Day 14 and Day 60
- Change of clinical status related to COVID-19 on Day 14 compared with baseline according to the NIAID 8-point ordinal scale as listed above
- Proportion of patients requiring invasive ventilation (mechanical ventilator and/or ECMO), or who are not alive on Day 14 or Day 28
- Proportion of patients in each category of the NIAID 8-point ordinal scale
- Time to (first) improvement of at least 1 category on the NIAID 8-point ordinal scale (until Day 28). Patients who did not improve at least 1 category on the NIAID scale or die before Day 28 will be censored at Day 28.
- The odds ratio between MP1032 and SoC and placebo and SoC for the number of patients with clinical status improvement from baseline on the NIAID 8-point ordinal scale (ie, an improvement of at least 1 category) at Day 14 and Day 28
- Total duration of hospitalization on Day 28 and Day 60 (from baseline to discharge; with death censored on the last day of the observed period at Day 28 or Day 60, respectively)
- Proportion of patients alive and testing negative for COVID-19 on Day 14, Day 28, and Day 60

This document is confidential.

Page 32 of 80

- Safety and tolerability assessed by:
 - Cumulative incidence of TEAEs (summarized by seriousness, severity, relationship to the study medication, outcome, and duration)
 - Vital sign parameters
 - Clinical laboratory parameters
 - Physical examination findings
- MP1032 plasma concentrations and PK parameters (if possible) including maximum observed plasma concentration, area under the concentration-time curve, elimination parameters, apparent body clearance, apparent volume of distribution, trough concentration, average observed plasma concentration at steady state, and other relevant PK parameters assessed via MP1032 plasma exposure on Day 1 and Day 7 in a PK subset of patients

Exploratory endpoints of this study are:

- Change in saturation of oxygen (SpO₂)/fraction of inspired oxygen (FiO₂) ratio (for patients alive) on Day 14 or Day 28 compared with baseline
- Total number of days in the intensive care unit (ICU)
- Duration of invasive mechanical ventilation
- Duration of ECMO

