- Time to recovery from COVID-19 symptoms (stuffy or runny nose, sore throat, red or irritated eyes, shortness of breath, cough, low energy or tiredness, muscle or body aches, headache, chills or shivering, feeling hot or feverish, nausea, and number of times of vomit, times of diarrhea, sense of smell, sense of taste in the last 24 hours) at Day 14, Day 28, and Day 60
- Change from discharge in the EuroQol (EQ) index value and EQ visual analog scale (VAS) based on the EuroQol-5D-5L (EQ-5D-5L) questionnaire at Day 60
- Change from baseline in biomarker levels potentially including, but not limited to, cytokines (eg, C-reactive protein, interleukin [IL]-1β, IL-6, TNF-α, and IFN-γ) and other coagulation/inflammatory biomarkers (eg, D-dimer and ferritin)

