This document is confidential.

Page 71 of 80

MetrioPharm AG MP1032

proportion of patients in each NIAID category, and the proportion of patients alive and testing negative for COVID-19 on Day 14, Day 28, and Day 60, respectively, will be compared between the treatment groups using MH test. Overall survival, time to (first) improvement of at least 1 category on the NIAID scale and total hospitalization duration (from baseline to discharge; with death censored on last day of the observed period – at Day 28 or Day 60, respectively – depending on the analyses) will be summarized using the Kaplan-Meier method and will be compared between treatment groups using log-rank tests. Additionally, Cox proportional hazards model will be applied with treatment and the 2 stratification factors as covariables.

The odds ratio between MP1032 and SoC and placebo and SoC for the number of patients with clinical status improvement from baseline on the NIAID 8-point ordinal scale (ie, an improvement of at least 1 category) at Day 14 and Day 28 will be analyzed using a logistic regression with consideration of the 2 stratification factors.

The time to recovery of all at baseline present COVID-19 symptoms (stuffy or runny nose, sore throat, red or irritated eyes, shortness of breath, cough, low energy or tiredness, muscle or body aches, headache, chills or shivering, feeling hot or feverish, nausea, and number of times of vomit, times of diarrhea, sense of smell, sense of taste in the last 24 hours) will be presented by Kaplan-Meier estimates and figure. The change from baseline will be presented in shift tables for each single symptom, with the number and percentage of subjects in each category at post-baseline assessment time-point compared to baseline for each treatment group.

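### The Kaplan-Meier curve for symptom recovery (exploratory) rests on assessments at Days 14, 28, 60 and discharge only, so between visits it reflects assessment and discharge timing

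*Protocol*

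**What the plan says.** Section 15.3 (Efficacy Analysis), with the same wording in the Bulgaria and France versions and in the France synopsis, takes as its variable "The time to recovery of all at baseline present COVID-19 symptoms" and states that it "will be presented by Kaplan-Meier estimates and figure". No interval-censored method is named, and no test is attached to this endpoint. Shift tables for each single symptom are planned alongside.

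On data collection, Section 11.1 states: "The assessment of the COVID-19 symptoms will be recorded at the visits specified in the Schedule of Assessments". In Table 1 the symptom row is marked at screening, Day 1, Day 14, Day 28, Day 60 and the day of discharge or early termination. Days 2 to 13 carry a dash, and Day 21 has no mark in the table as it can be read here. The row for the NIAID scale, by contrast, is marked for Days 2 to 13. Visit windows are ±2 days at Day 14 and ±3 days at Days 28 and 60.

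Section 6.2 lists this item under "Exploratory endpoints of this study are" and ends its description with "sense of taste in the last 24 hours) at Day 14, Day 28, and Day 60". The patient diary is no second source of dates: Section 9.5 says that "treatment compliance will be conducted via a diary". The questionnaire in Table 2 asks about current symptoms or the last 24 hours. It never asks when a symptom ended.

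**The concern.** A Kaplan-Meier curve treats each event time as known. Here a recovery is known only to have happened between two assessments, which can be as far apart as Day 28 and Day 60 (32 days). Dating it to the assessment that first finds the patient symptom-free shifts the curve to the right and turns it into steps at visit days.

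The discharge assessment adds a second problem. It is an extra look whose timing depends on how the patient is doing, and duration of hospitalization is itself a secondary endpoint that treatment may change. If one arm goes home earlier, its recoveries are also recorded earlier, even if symptoms end at the same time in both arms.

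The protocol fixes both the sparse schedule and the estimator. A statistical analysis plan could name a different estimator, but it could not restore dates that are not collected. What is at stake is how an exploratory figure is read in a proof-of-concept trial. No primary or secondary conclusion depends on it.

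**Working it through.** **The plan's own figure.** None is stated for symptom recovery. The only design calculation, 83% power for the primary endpoint with 76 and 38 patients, is reproduced (0.8301 by the uncorrected chi-square formula) but has no bearing here.

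**Inputs.** From the protocol: assessments at Days 14, 28, 60 and discharge; windows of ±2 and ±3 days; 80 and 40 patients. Assumed, because the protocol gives no values: exponential recovery with median m, and lognormal discharge day (log-SD 0.5 unless stated).

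**1. Scheduled visits only, held on the nominal day.** The true proportion recovered by day t is F(t) = 1 − 2^(−t/m). Nothing is recorded before Day 14, and on Day 14 the curve jumps to F(14) = 1 − 2^(−14/m). This is at least 50% whenever m ≤ 14, so every true median up to 14 days is recorded as 14. By the same argument, every true median above 14 and up to 28 is recorded as 28. True medians of 6 versus 10 days, or 7 versus 12, both give 14 versus 14; 16 versus 24 gives 28 versus 28.

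**2. Delay, with the discharge look included.** Recorded time is the first assessment at or after true recovery. For true medians of 8 to 12 days and median discharge on Day 8, simulation gives a mean delay of about 7 to 8 days.

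**3. Discharge timing alone.** Both arms have the same true median of 10 days; discharge medians are 8 and 12 days.

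| By day | True, both arms | Recorded, discharge median 8 | Recorded, discharge median 12 |
|---|---|---|---|
| 10 | 1 − 2^(−1.0) = 50% | 25% | 15% |
| 13 | 1 − 2^(−1.3) = 59% | 34% | 26% |
| 14 | 1 − 2^(−1.4) = 62% | 62% | 62% |

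The gap before Day 14 is produced by discharge dates and closes at the Day 14 visit. The Day 10 row does not depend on the visit window, because the earliest Day 14 visit is Day 14 − 2 = Day 12.

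**4. Effect of the visit windows on a median.** True medians 8 versus 12 days, 80 and 40 patients, median discharge on Day 8:

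- Visits exactly on the nominal day: both medians equal 14 in 44%, 76% and 78% of trials for discharge log-SD 0.3, 0.5 and 0.7.
- Visits spread evenly over the protocol's windows: both equal 14 in about 2% to 10%, and the medians tie in about 9% to 15%. The typical difference is 2 days, against a true difference of 12 − 8 = 4.

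The windows therefore remove most exact ties but leave the difference compressed.

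**The case against.** The strongest reply is that little depends on this figure. The endpoint is exploratory, and Section 15.3 gives log-rank tests and Cox models to survival, NIAID improvement and hospitalization duration but no test to symptom recovery. The protocol names no median for it. Section 6.2 ties the endpoint to Days 14, 28 and 60, and at about those days the curve gives the proportion with recorded recovery. All of this stands and sets the weight of the point.

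A reader might infer that the curve says nothing about recovery, or that the two arms' medians would coincide in most trials and hide a real effect. The documents do not support either reading. The first fails at the scheduled visits. The second needs every visit on its nominal day, contrary to the windows in Table 1. Comparative information also largely survives: for true medians of 8 versus 12 days, F(14) is 1 − 2^(−14/8) = 70% versus 1 − 2^(−14/12) = 55%. In simulation, a log-rank test at the 10% level (not planned; used only as a gauge) rejects in 57% of trials with visit-dated times, against 63% to 65% with true times.

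Two further replies carry less weight. The shift tables go symptom by symptom, so they do not give the proportion with all baseline symptoms resolved. The false early gap does rest on an assumed 4-day difference in median discharge, but discharge is an outcome the trial itself compares, so such a difference cannot be ruled out.

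One caution limits the remedy. An interval-censored (Turnbull) estimate assumes that assessment times are unrelated to recovery. Including the discharge assessment would bring the same defect back.

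**Conclusion.** The point holds as a minor one on an exploratory, descriptive endpoint. The named estimator does not fit the data collected: recorded recovery is late by about a week on average, any reported median is drawn towards a visit day, and between visits a difference in discharge timing can look like a difference in symptom recovery. The curve can be trusted only at about Days 14, 28 and 60.

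The mismatch follows from the protocol alone. The sizes rest on assumed exponential recovery (medians 8 to 12 days) and lognormal discharge; the 25% versus 15% at Day 10 also needs discharge medians of 8 versus 12 days. A lost Day 21 mark in Table 1 would split one interval and leave the conclusion unchanged. The primary and secondary analyses are unaffected.

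**What to change.** In Section 15.3 of both country versions, and in the synopsis where it repeats the text:

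- Make the main summary the proportion of patients alive with all baseline symptoms resolved at the Day 14, Day 28 and Day 60 visits, by arm. Give the stratified Mantel-Haenszel risk difference and confidence interval already used for the other binary endpoints. Define resolution by status at the visit, so that the discharge assessment plays no part.
- Report no Kaplan-Meier median for this endpoint.
- If a curve is kept, use an interval-censored estimate built from the last symptomatic and first symptom-free scheduled visit, at actual visit dates. Exclude the discharge assessment, because its timing depends on outcome.

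The cost is a wording change, with no new data and no change to sample size. The downside is that there is no single median time to recovery to quote.

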5.4 Safety Analysis

All safety parameters will be summarized descriptively by treatment group for the entire study period.

Study drug duration and SoC therapies will be described for each treatment group.

This document is confidential.

Page 73 of 89

All reported AEs will be coded into preferred term (PT) and grouped by SOC using the most recent Medical Dictionary for Regulatory Activities version. An overall summary will be provided with the number and percentage of patients reporting TEAEs, serious TEAEs, treatment-related TEAEs, TEAEs leading to withdrawal, and TEAEs leading to death. For patients with any serious TEAE and for patients with any related serious TEAE exposureadjusted events rates will be calculated and compared between treatment groups using the risk ratio [(300 mg MP1032 BID plus SoC) / (placebo plus SoC)] with respective 95% confidence intervals. This comparison will also be performed for the rate of re-hospitalization which is considered a serious AE. The number and percentage of patients with TEAEs, serious TEAEs, TEAEs leading to withdrawal, and treatment-related TEAEs will be summarized by SOC and PT for each treatment group, and total. In these tables, the incidence of TEAEs by SOC and PT will also be included. TEAEs will also be summarized by maximum severity and relationship to study drug. Events with missing onset dates will be considered as TEAEs. If a patient experienced >1 occurrence of the same AE, the occurrence with the greatest severity and the closest association with the study drug will be used in the corresponding summary tables. In case that for one AE several AE episodes with changing severity is reported, an aggregation of all respective episodes to one AE will be performed before summarization. The worst severity and the worst causality will be assigned to the aggregated AE and used for the respective AE summaries. All reported AE episodes will be listed by patient, along with information regarding onset, duration, severity and relationship to study drug, action taken with study drug, treatment of event, and outcome. Additionally, the aggregated AEs with the resulting worst severity and worst relationship will be included in the AE listings.

Vital signs including SpO₂ (%) will be summarized using descriptive statistics, including mean values and mean change from baseline values. Clinical laboratory data of local laboratories will be presented with the number and percentage of patients with values below, within, or above the normal range at each time point. Additionally, a shift table of the number and percentage of patients with normal and abnormal, and clinically significant abnormal values at each scheduled postbaseline visit compared with the normal/abnormal/clinically significant abnormal categorization at baseline will be provided by treatment group. Summarizing of clinical laboratory data of local laboratories using descriptive statistics, including mean values and mean change from baseline values will be only possible after normalization of the values using a reference laboratory. Details for normalization will be provided in the SAP.

Summary tables will be provided for concomitant medications.

